This study will be an open-label, randomized, 2-arm clinical trial. 620 children will be enrolled and randomized at 6 months of age to one of two study arms. The primary objectives of this study are to assess the immunogenicity of MR vaccine at 6 months, and assess equality of MR vaccine seroconversion administered at 9 months following administration of an earlier MR vaccine dose at 6 months of age compared with MR vaccine dose administered at 9 months only without previous MR vaccination. The study will enrol generally healthy 6 month old infants living in Matlab and who have never received an MR vaccine dose and have no history of measles or rubella. Participants will be followed to 11 months of age.

Infants in this study will be randomly assigned to one of two arms. Infants in Study Arm A will receive MR vaccine at 6 months of age (at enrolment) and at 9 months. Infants in Study arm B will receive MR vaccine only at 9 months.

Blood specimens will be collected from all infants at 6, 9 and 11 months of age. The 6 month sample is a pre-vaccination sample and mainly will be used to determine maternal antibody levels. For arm A, the sample collected at 9 months before the second MR dose will be used to assess antibody levels after the first MR dose at 6 months of age. For study Arm B, the 9 month sample will be used to assess measles and rubella antibody decay rate. The sample collected at 11 months will be used to assess immune response to either a two dose or a one dose schedule (arms A and B, respectively). The study design and participant evaluations are illustrated in the Table.

Table: Schematic representation of study arms

Arm		Age of participant				
		6 months	9 months	11 months	Sample size	Enrollment target (sample size + 10% attrition)
A	MR 6 & 9 months	MR •	MR •	•	279	310
B	MR 9 months	•	MR •	•	279	310
	Total (infants)				558	620
	Mothers	•			558	620

• Indicates blood collection
MR- Measles -rubella vaccination

Blood specimens will be collected from mothers of all enrolled infants at time of enrolment.

Study enrolment and withdrawal

A sample of 620 infants at age 6 months (180 days, +/- 7 days) of age (310 per each study arm) will be enrolled from population living in Matlab area. Inclusion and exclusion criteria are provided below.

Inclusion criteria: Infants

- Healthy infants at 6 months (180 days, +/- 7 days) of age (calendars will be provided to staff)

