Immune response is defined as a 4-fold increase in antibody titers 12 weeks after vaccination (post-6-month visit) compared with 6-month pre-vaccine titers accounting for the expected decline in maternal antibody titers or a change from antibody-negative to positive (i.e. seroconversion). In addition, quantitative data on antibody titers will allow us to assess the magnitude of seroresponse show as $-N$ -fold increases of pre- and post-vaccine titers. Seroprotection is defined as titer of ≥ 120 mIU/mL for measles and rubella >10 IU/mL

Secondary outcomes:

Several secondary outcomes will be assessed:

- 1) Secondary outcome is based on measles titers by MBA (mIU/ml) and rubella titers (IU/mL) by ELISA on sera collected 8 weeks after MR 9-month dose of vaccination (i.e., at 11 months) – post two dose series for participants in Arm A and 1 dose for arm B.
- 2) The safety profile of MR vaccine will be assessed by incidence of specific symptoms/problems. They will be categorized into one of the following three categories:
 - a) Immediate reactions (with emphasis on allergic reactions), occurring in the first 30 minutes post vaccination observed by study staff at the fixed site clinic.
 - b) Adverse events (AE) following 6-month MR dose that may occur during the 48 hours after 6-month MR vaccine administration. AEs will be graded and subcategorized as those deemed related to vaccination or not by the investigator.
 - c) Serious adverse events (SAEs) occurring from vaccination during the course of the study, identified or observed by study staff and/or reported by parent at any time during the study period. SAEs will be subcategorized as those deemed related to vaccination or not by the investigator and reviewed by the local Data and Safety Monitoring Board (DSMB) and icddr,b ERC committee.

Data Analysis

This is an open-label trial clinical trial that compares immunogenicity of MR vaccine schedules. The study will recruit 620 participants in 2 arms. Participants will be enrolled at 6 months of age and followed at 9 months and 11 months of age for a total of 5 months of follow-up.

General analytical issues

The data will be analysed by study investigators that include epidemiologists and statisticians. Statistical packages that would be used for the analysis include R, SAS and STATA.

The immunogenicity of each MR vaccination schedule will be determined by measuring antibody levels:

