- Compare the proportion of participants demonstrating seroconversion at 9 months in both study arms. We will use chi-square test to test for statistical significance
- Compare the change in median titers of measles and rubella antibodies by study arm
- Compare immunogenicity of MR vaccine administered at 6 months (Arm A) vs 9 months (Arm B). Analyse the relationship of infants' immunogenicity to MR vaccine and mothers' level of antibodies
- Analyse the relationship between the levels of infants' maternal measles and rubella antibodies and mothers' antibodies
- Analyse results of adverse events by study arm and compare by age and arm of the study.

Data Safety Monitoring Plan (DSMP)

Records to be kept

Participant data will be collected using case report forms (CRFs). Personal identifiers will not be recorded on any CRFs, biological specimens or electronic records. Participants will be identified by a participant identification number (PID), which will be provided after enrolment and randomization. The PID will be used to link information recorded in CRFs and results from laboratory analysis of biological specimens.

Data entry, cleaning and storage

Records of participants will be kept in a locked cabinet with access restricted to study staff and investigators. All computer records will be kept in a locked room. The computers will be password protected. Only the study staff and investigators will be authorized to access the digital records.

Data from the CRFs will be entered into an electronic database. Checks will be performed to identify and correct data entry errors. After the completion of analysis and publication of study results, the study forms and database will be archived. The forms will be stored in a locked cabinet with access restricted to investigators. The database will be password protected.

Site monitoring plan

Prior to start of the study, Standard Operating Procedures (SOPs) will be developed by investigators in consultation with study staff. Study staff will be trained in study procedures and human subjects' management. After start of the study monitoring of study site will be conducted twice.

During these monitoring visits the following study documents and procedures would be reviewed:

1. Participant records, including consent forms
2. CRFs and other supporting data
3. Adverse event forms
4. Data Safety and Monitoring Board (DSMB) reports
5. Laboratory specimen records
6. Vaccine and biological materials storage and records

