All participants will be observed for 30 minutes post vaccination to monitor for any immediate adverse reactions to the vaccine. Properly skilled medical personnel will be immediately available in case of an emergency in the event of an unexpected adverse reaction. The study physician will record at the end of this period the presence of any potential reaction to the vaccine. At the end of each study visit, the physician or study coordinator will provide the parents with a phone number for a study nurse to call if they have any questions or experience any reactions to the vaccine.

A study staff will visit the house of the participant to inquire and record any potential adverse event in 48 hours after the first dose of MR administered at 6 months (study arm A).

Should a serious illness occur while enrolled in the study (requiring a physician's visit or hospitalization), parents will be instructed to seek medical care immediately. Medical care for expected

minor illnesses that will develop during the follow up period in study participants such as rash, fever or respiratory infections as well as any adverse outcomes of the vaccination judged to be possibly, probably or definitely related (detailed below) to study vaccines or vaccination will be provided free of charge.

Recording, monitoring and reporting of adverse events

During each study visit the study staff will question the parents of the participant about possible adverse events (AE) since the previous study visit and record this in the CRF. Reported AE will be recorded in the AE form. The AE form will include a description of the event, time of onset, assessment of severity, relationship to study product, and time of resolution/stabilization of the event.

Reports of AE will be periodically discussed by the team of investigators. The study team will review the potential relationship and classify the relationship into:

1. Unable to judge
2. Not related
3. Probably not related
4. Possibly related
5. Probably related
6. Definitely related

Interpretation of vaccine-relationship to AE will be based on the type of event, the relationship of the event to the time of vaccine administration, the known biology of the vaccine and the investigators' medical judgment.

An AE will be considered a serious adverse event if it meets any of the following criteria:

1. Death during the study period
2. Hospitalization
3. Anaphylaxis associated with vaccine administration

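### The serious adverse event outcome is tied to vaccination, which conflicts with other sections on whether Arm B counts before 9 months, and no MR-versus-no-MR comparison at 6 to 9 months is specified

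*Combined protocol and SAP*

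**What the plan says.** **Outcome.** In the protocol's Secondary outcomes, item 2(c) covers "Serious adverse events (SAEs) occurring from vaccination during the course of the study, identified or observed by study staff". The same sentence extends to events "reported by parent at any time during the study period", and the item adds that "SAEs will be subcategorized as those deemed related to vaccination or not by the investigator".

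**Dosing and follow-up.** Under Study design, "Infants in Study Arm A will receive MR vaccine at 6 months of age (at enrolment) and at 9 months"; Arm B has the 9-month dose only. Under Data Analysis, infants are "followed at 9 months and 11 months of age for a total of 5 months of follow-up".

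**Time frame.** Time to endpoint gives the first secondary (safety) endpoint a window from randomisation to 11 months, but links it to reactions after the 6-month dose, which only Arm A receives.

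**Collection.** The section Recording, monitoring and reporting of adverse events sets no restriction by arm: "During each study visit the study staff will question the parents of the participant about possible adverse events (AE) since the previous study visit". The SAE criteria there include "Death during the study period" and hospitalisation, neither linked to a dose. Every SAE is notified to regulators, ethics committees and the DSMB.

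**Analysis.** The list of comparisons that closes the analytical approach says: "Analyse results of adverse events by study arm and compare by age and arm of the study". It gives no window, denominator or test for adverse events.

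**The concern.** From 6 to 9 months Arm B is a randomised, concurrent, unvaccinated control for the early dose. Deaths and hospital admissions happen in infants of this age whatever they receive, so this control is what separates background illness from an effect of the 6-month dose.

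An outcome that starts at vaccination removes it. A hospitalisation at 7 months would count in Arm A and not in Arm B. A simple tabulation by arm would then show more SAEs in Arm A even if the vaccine did nothing, and interpretation would lean on relatedness judgements made in an open-label trial.

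This is separate from the Arm A-only home visit. It would arise even if both arms were followed identically.

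**Working it through.** **1. The plan's own figures.** Follow-up is 11 − 6 = 5 months, as stated. The enrolment target is 279 / (1 − 0.10) = 310 per arm, as stated.

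**2. Time at risk, by reading of 2(c)** (310 per arm, attrition ignored):

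| Reading | Arm A | Arm B | Ratio |
|---|---|---|---|
| From first dose to exit | 310 × (11 − 6) = 1,550 infant-months | 310 × (11 − 9) = 620 | 2.5 |
| From randomisation to exit | 310 × 5 = 1,550 | 310 × 5 = 1,550 | 1.0 |
| From randomisation to the 9-month visit | 310 × (9 − 6) = 930 | 930 | 1.0 |

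On the first reading, 930 of Arm B's 1,550 infant-months (60%) lie outside the outcome. With 279 per arm the figures are 1,395 and 558, with the same ratio.

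**3. Which reading do the documents support?**

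- If *from vaccination* means after vaccination, Arm B events before 9 months are out. Items 2(a) and 2(b) are also anchored to a dose, and the secondary hypothesis (Hypothesis to be tested) compares post-immunisation reactions after Arm A's two doses with those after Arm B's one.
- If it means caused by vaccination, those events are out again, since no dose has been given. This fits poorly with keeping SAEs judged unrelated.
- Against both stand the whole-study phrase within 2(c), the randomisation-to-11-months time frame, and SAE criteria and questioning that do not depend on a dose.
- The analysis by age and arm could separate 6–9 from 9–11 months. It could equally mean reactions to a dose given at 6 months against one given at 9 months. It does not say.

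So Arm B events at 6–9 months are planned to be collected and notified. Whether they enter the analysed outcome is not settled.

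**4. Illustration only.** The documents give no background SAE rate. Assume a constant rate r per infant-month and no vaccine effect. On the first-dose reading, the expected number of infants with an SAE is 310 × (1 − exp(−r × months)):

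| r (assumed) | Arm A, 5 months | Arm B, 2 months | Ratio |
|---|---|---|---|
| 0.25% | 3.9 | 1.5 | 2.49 |
| 0.5% | 7.7 | 3.1 | 2.48 |
| 1% | 15.1 | 6.1 | 2.46 |
| 2% | 29.5 | 12.2 | 2.43 |

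The ratio hardly depends on r; the counts do.

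**5. What the 6–9 month comparison would deliver.** With p = 1 − exp(−3r) in each arm, the approximate 95% half-width of the risk difference is 1.96 × √(2p(1 − p)/310). For r = 0.25%, 1% and 2%, p is 0.75%, 2.96% and 5.82% (2.3, 9.2 and 18.1 infants per arm). The half-width is about 1.4, 2.7 and 3.7 percentage points. This is modest precision, but the contrast is randomised and over equal time.

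**The case against.** The strongest reply is that 2(c) should be read as a whole and alongside the other sections. It allows reports at any time in the study, keeps unrelated SAEs, and sits with a safety endpoint timed from randomisation. On that reading both arms have 5 months and the imbalance disappears. This stands as a legitimate reading, but it does not settle the matter. The reporting phrase can describe when an event may come to notice, and the endpoint's time frame is attached to reactions after a dose that Arm B does not receive at 6 months.

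A reader might infer something stronger: that the plan discards the Arm B control and builds in a 2.5-fold false excess with a calculable false-positive rate. The documents do not support that. No section says Arm B events before 9 months are excluded, and no comparison of Arm A's 5 months with Arm B's 2 is planned. The chi-square test is named only for immunogenicity and seroconversion, so no false-positive rate for SAEs can be attributed to the plan.

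Nor is the 6–9 month contrast wholly free of bias. The trial is open-label, and only Arm A has the 48-hour home visit. That affects mainly non-serious events; deaths and hospital admissions are less open to it.

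**Conclusion.** The point holds as a conflict and an omission. Item 2(c), read literally, excludes Arm B's first 3 months, whereas Time to endpoint and the adverse-event recording section point to the whole study in both arms. Under any reading, the plan states no SAE window or denominator and does not specify the randomised MR-versus-no-MR comparison at 6–9 months.

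The 1,550 against 620 infant-months applies only if the outcome clock starts at first dose. The expected counts also rest on assumed background rates, a constant hazard and no attrition. Neither is an established bias of the planned analysis. The change is still worth making: it removes the ambiguity and uses a comparison that the design already provides.

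**What to change.** - Restate 2(c) as all SAEs on the protocol's own criteria (death, hospitalisation, vaccine-associated anaphylaxis) from randomisation to the 11-month visit, in all randomised infants in both arms. Keep relatedness as a sub-category.
- State that the denominator is all randomised infants. The Primary analytical approach limits primary and secondary objectives to infants with adequate blood at 6, 9 and 11 months. If that applied to safety, infants who died or left early would drop out.
- Specify the main safety comparison: arms as randomised, from randomisation to the 9-month visit before that day's dose, with a risk difference and 95% CI.
- Report 9–11 months separately by arm, and do not set Arm A's 5 months against Arm B's 2.
- Align Time to endpoint and the adverse-event line of the analysis list with this wording.
- Note that the Arm A-only 48-hour home visit makes ascertainment unequal, mainly for non-serious events.

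The cost is a change of analysis wording. No extra visits are needed, provided the planned questioning at each visit was carried out in both arms. The section on laboratory assays says field data collection is complete, so the amendment should be dated and should state what SAE data by arm had already been seen.

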4. To determine the extent of variation in measles antibodies in women of child bearing age in a population with a long standing measles vaccination program
5. To determine the extent of variation in rubella antibodies in women of child bearing age in a population where rubella vaccine have been recently introduced
6. To determine if variation in antibody levels in infants at 6 months is predominately explained by variation in starting antibody levels in the mother in this population
7. To estimate the half-life of decay of measles and rubella antibodies in infants

Methods:

This study will be an open-label, randomized, 2-arm clinical trial in healthy infants in Bangladesh. 620 children will be enrolled and randomized at 6 months of age to one of two study arms. The study design and participant evaluations are illustrated in Table.

Table: Schematic representation of study arms

Arm		Age of participant				
		6 months	9 months	11 months	Sample size	Enrollment target (sample size + 10% attrition)
A	MR 6 & 9 months	MR •	MR •	•	279	310
B	MR 9 months	•	MR •	•	279	310
Total (infants)					558	620
	Mothers	•			558	620

• Indicates blood collection
MR- Measles -rubella vaccination

Outcome measures/variables:

The primary end-point assessment will be based on **measles antibody titers (mIU/ml) (measured by the multiplex bead assay (MBA))** and rubella titers (IU/mL) (measured by ELISA) on sera collected 8 weeks after completion of vaccination series (at 11 months of age). Immune response is defined at 8 weeks after completion of vaccination series, as seropositivity post-vaccination if pre-vaccination antibody was undetectable (i.e. seroconversion), or a 4-fold or greater increase in antibody titers among pre-vaccination seropositives after adjusting for decline in maternal antibodies. Seroprotection is defined as antibody level of ≥ 120 mIU/mL for measles and >10 IU/mL for rubella. We will calculate the proportion of children attaining post-vaccination protective levels of antibodies.

Description of the Research Project

Hypothesis to be tested

Does this research proposal involve testing of hypothesis: No Yes (describe below)

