Some researchers suggest that routine MCV should be given before age of 9 months based on published data showing that infants born to mothers with vaccine induced measles immunity are born with lower concentration of maternal measles antibodies (MMA) and lose protection against measles infection at an earlier age. (10, 26) Measles vaccine immunogenicity depends on several factors, including presence of maternal measles antibodies (i.e., passively acquired measles antibodies may neutralize vaccine virus before a complete immune response develops resulting in primary vaccine failure.), maturity of immune system of the vaccine recipient, and strain of the measles vaccine used. So any decisions to alter the age of MCV1 dose should balance the potential risk of primary vaccine failure against the risk of measles infection and measles related complications, including death. Immunogenicity of measles vaccine given at 6 months is well studied; however, data on immunogenicity of combined MR vaccine administered at 6 months and its impact on MR vaccine effectiveness given at 9 months, is limited.

Because the number of infants born to mothers with vaccine induced immunity has been steadily increasing and most countries will be using MR vaccine routinely in EPI, it is timely to conduct a study to assess immunogenicity of MR vaccine given at 6 months and its impact on a subsequent 9 month MR dose. The first dose of MCV given at 6 months is frequently referred to as MCV0, indicating that two subsequent doses are needed to attain population seroprotection levels necessary to stop endemic transmission of the measles virus.

To improve the accuracy of interpretation of study results it would be prudent to test mothers of enrolled infants for measles and rubella antibodies. Without the knowledge of maternal antibody status it would be difficult to interpret results of the infants with low or undetectable levels of maternal antibodies. Testing maternal serum samples would help us to understand whether low or undetectable baselines are due to decay or absence of maternal antibodies. This will also enable us to determine the proportion of mothers with undetectable, detectable and protective levels of antibodies, and to assess the relationship between the level of antibodies in mothers and their infants' maternal antibodies.

Research Design and Methods

Setting: Study area

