A major limitation of many studies in which mother-infant paired serum samples were tested, was ascertainment of mothers' past measles or rubella vaccination or measles and rubella natural infection status. Some authors used age (i.e., year of birth, born in pre- measles or rubella vaccination era) as a proxy for determining the past vaccination or disease status. One recent study minimized recall bias as the researchers ascertained mothers' status (vaccine induced or post-infection antibodies) by reviewing their medical charts. [4]

Primary analytical approach

Intention-to-treat (ITT) analysis will be conducted on all enrolled participants who are randomized and receive two measles-rubella vaccines (at 6 and 9 months, study arm A) or one measles-rubella vaccine dose (at 9 months, study arm B).

Children who are seropositive ($\geq 1:120$ mIU/mL) for measles before vaccine administration (at 6 months of age, study arm A; at 9 months, study arm B) will be included in the ITT analyses and will be included in the safety analysis. Similarly, children who are seropositive (≥ 10 IU/mL) for rubella before vaccine administration (9 months of age) will also be included in the ITT analyses.

To evaluate primary and secondary objectives, the analysis will be restricted to participants who

- Have not withdrawn consent for receipt of MR vaccine and follow-up evaluations since enrolment
- Have adequate blood specimen for serological analysis from the enrolment visit, and
- Have adequate blood specimen for serological analysis from study site visits at 6, 9 and 11 months of age (For presence of maternal measles and rubella antibodies – 6 months, seroconversions: 9 months of age and 11 months)

Secondary analytical approach

In addition, we will also perform a per protocol analysis.

To evaluate primary objective, per protocol analysis will be restricted to participants who

- Have not withdrawn consent for receipt of vaccines and follow-up evaluations since enrolment
- Have adequate blood specimen for serological analysis from each visit within 3 days of 6, 9 and 11 months of age, and
- Have received all scheduled vaccines within 3 days of scheduled visit date

Using the above described primary analytical approach we will

- Compare the proportion of participants demonstrating immunogenicity in response to measles and rubella vaccines across study arms and use chi-square test to test for statistical significance across study arms.

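### The arm comparisons are unadjusted chi-square tests with no stated effect estimate or interval, although the infant's 6-month titre is available for adjustment: a modest loss of precision, not a bias

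*Combined protocol and SAP*

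**What the plan says.** The planned comparisons are listed at the end of the Secondary analytical approach subsection of Data Analysis. For the proportion showing a response to each antigen, the plan will "use chi-square test to test for statistical significance across study arms". A second item reads "Compare the proportion of participants demonstrating seroconversion at 9 months in both study arms. We will use chi-square test to test for statistical significance". Neither names a covariate, and no risk difference, ratio or confidence interval is specified. Randomization procedures describes random block sizes and a 1:1 ratio, with no stratification by titre.

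The protocol itself identifies a prognostic baseline variable. Study Rationale states: "Measles vaccine immunogenicity depends on several factors, including presence of maternal measles antibodies", and explains that "passively acquired measles antibodies may neutralize vaccine virus before a complete immune response develops". Study design says of the first infant sample: "The 6 month sample is a pre-vaccination sample and mainly will be used to determine maternal antibody levels". Primary analytical approach limits the analysis to infants who "Have adequate blood specimen for serological analysis from the enrolment visit" and who "Have adequate blood specimen for serological analysis from study site visits at 6, 9 and 11 months of age".

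The 6-month titre has two other uses. It enters the response definition, which for infants who start seropositive is a "4-fold or greater increase in antibody titers among pre-vaccination seropositives after adjusting for decline in maternal antibodies" (Project Summary, Outcome measures/variables). General analytical issues also promises an assessment of how maternal antibody affects immunogenicity of the 9-month dose, without naming a model. Neither makes the titre a covariate in the arm comparison.

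**The concern.** A baseline variable that predicts the outcome, is measured before vaccination and is present for every analysed infant can narrow the interval for the arm difference and remove the effect of chance imbalance, with no extra blood draw or infant. The plan does not use it that way.

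The missing estimate matters separately. The study hypothesis is that the two schedules are not different. A chi-square p-value cannot show that; a risk difference with an interval at least shows which differences remain compatible with the data. Such an interval can be had without adjustment, and adjustment supplies no equivalence margin. The specific cost of leaving out the titre is therefore precision, and the question is how much.

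**Working it through.** **Inputs.** Sample size section: 75% response in Arm B, 65% in Arm A, 80% power, 279 per arm, inflated to 310. Alpha and sidedness are not stated there; the calculation is described only as an equality comparison. The correlation r is not given, so 0.2, 0.3 and 0.4 are assumed.

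**The plan's own figure.** With mean proportion 0.70 and pA·qA + pB·qB = 0.2275 + 0.1875 = 0.415,

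n = [z_α √(2 × 0.70 × 0.30) + 0.842 √0.415]² / 0.10².

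- One-sided 5%: 258.6, so 259; with continuity correction 278.3, so 279.
- Two-sided 5%: 328.5, so 329; with continuity correction 349.
- Attrition: 279/0.90 = 310.

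Thus 279 reproduces with a one-sided 5% level (equally, two-sided 10%) plus continuity correction.

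**Unadjusted power at 279 per arm, two-sided 5%.**

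Φ[(0.10 − 1.96 √(0.42/279)) / √(0.415/279)] = Φ[(0.10 − 0.0760)/0.0386] = 73.3%.

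At one-sided 5%, without continuity correction, it is 82.6%. The 95% interval for the difference has half-width 1.96 × 0.0386, about 7.6 percentage points.

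**Adjusted, titre equally predictive in both arms.** Variance falls by r² and the effective size is 279/(1 − r²).

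| r | Variance reduction | Effective n per arm | Gain per arm | Power, two-sided 5% |
|---|---|---|---|---|
| 0.2 | 4% | 291 | 12 | 75.0% |
| 0.3 | 9% | 307 | 28 | 77.2% |
| 0.4 | 16% | 332 | 53 | 80.4% |

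**Adjusted, titre predictive in Arm A only.** At 1:1 allocation the common fitted slope is about half Arm A's slope. Treating the arm variances as equal (σ²), Arm A's variance falls by ¾r²σ² and Arm B's rises by ¼r²σ². The net fall is ½r²σ² out of 2σ², or r²/4.

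| r in Arm A | Variance reduction | Effective n per arm | Gain per arm | Power, two-sided 5% |
|---|---|---|---|---|
| 0.2 | 1.0% | 282 | 3 | 73.7% |
| 0.3 | 2.3% | 285 | 6 | 74.2% |
| 0.4 | 4.0% | 291 | 12 | 75.0% |

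Using the unequal variances 0.2275 and 0.1875 gives gains of 3, 7 and 13. An arm-by-titre interaction recovers no more at 1:1.

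**Simulation check** (3,000 trials per setting, titre acting in both arms). Two-sided power, chi-square against adjusted logistic, was 73.7% against 77.9% when the titre explained about 9% of outcome variance, and 73.2% against 80.3% at 15.5%. With no arm difference, rejection rates were 5.0% and 4.6%.

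**Which r is plausible?** Suppose a share s of infants is seropositive at 6 months and responds d lower. The explained share of variance is s(1 − s)d²/0.21. Passive immunity cites 1993 Matlab data with 67% below the protective threshold by 5 months, so 33% above it. Taking s from 5% to 33% and d from 20 to 40 points (both ranges assumed) gives about 0.01 to 0.17 if the effect acts in both arms. If it acts in Arm A alone, a quarter of that: about 0.002 to 0.04.

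**The case against.** The case for leaving the plan alone is strong in several respects.

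- **Validity.** A reader might infer that the unadjusted test is biased or invalid. It is not: under randomisation it keeps its type I error, and the simulation agrees.
- **Size.** A reader might infer that adjustment restores 80% power. That needs r near 0.4 in both arms. Arm B is first vaccinated at 9 months, when the Bangladesh study cited under Special Assays or Procedures found measles seroprotection of only 0.42% to 1.25%. The Arm A-only figures may therefore be nearer the truth. The same section allows that most infants may have no detectable antibody at 6 months.
- **Baseline power.** The 73.3% depends on a two-sided 5% test that the plan does not state. Any shortfall against 80% is a separate sample-size matter.
- **Use of the titre.** A reader might infer that the plan ignores it. It does not, since the titre enters the response definition and a separate assessment. Only the test leaves it out.
- **Cost.** The assay amendment says field data collection is complete, so a change needs a documented amendment. For rubella, the Measles-rubella vaccine section cites 100% seroprotection after a 9-month dose. If true response were 99.5% to 99.9% (assumed), an arm of 279 would contain no non-responder with probability 0.995^279 = 25% to 0.999^279 = 76%. Ordinary logistic regression would then give no finite arm estimate.

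All of this stands. It limits the size of the point and shapes the remedy. It gives no reason to omit an effect estimate, or a pre-specified measles model whose cost is small even if r proves low.

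**Conclusion.** The point holds as a recommended improvement, not an error that must be corrected. The between-arm tests omit a pre-vaccination covariate that the protocol names as a determinant of response and holds for every analysed infant, and no effect estimate or interval is specified. At an assumed two-sided 5% level, adjustment is worth about 2 to 7 points of power if the titre predicts equally in both arms, and about 0.4 to 2 points if only in Arm A. These ranges rest on an assumed r of 0.2 to 0.4 and on the planning rates of 75% and 65%. The documents do not support a claim of bias or of a large assured gain.

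Two qualifications apply. The covariate is complete only because randomised infants lacking any of the three specimens are excluded. It is drawn after arm assignment (Enrolment visit, steps 5 and 7), though before vaccination, so vaccination cannot have altered it.

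**What to change.** Before arm-level results are seen, amend Data Analysis as follows.

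1. **Measles, 11 months.** Logistic regression of response on arm and log 6-month infant measles titre, with an indicator for values below one named assay cut-off. The text now carries both 120 and 153 mIU/mL, so the choice must be stated. Report the standardised risk difference with 95% CI, and keep the chi-square as supportive.
2. **Rubella, 11 months.** Report the unadjusted risk difference with a score-type 95% CI, or use a penalised model if an arm has few or no non-responders. Fix the choice in advance.
3. **Status of the 11-month comparison.** State whether it is primary. The Project Summary and Time to endpoint treat it as primary; the later Secondary outcomes list places it among the secondary outcomes.
4. **Mother's titre.** Use it only in a secondary model, because the maternal exclusion criteria allow an infant to enrol without a maternal sample.

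The cost is a documented amendment and one extra model per antigen, with no new data.
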